### 1.2 Vascular Occlusion in the Pathogenesis of Sickle Cell Complications

SCD is associated with a number of serious and potentially disabling conditions that have similar symptoms but vary in severity by genotype. The most notable complication of SCD is VOC, an extremely painful and serious consequence of SCD presumably resulting from acute ischemic tissue injury. Individuals with the SCD-SS and SCD-S $\beta^0$ -thal genotypes tend to experience similar disease severity, which is more severe than for other genotypes. SCD-SC and SCD-S $\beta^+$ -thal are associated with a milder form of sickle cell disease.

Over the course of a year, about 60% of patients with SCD-SS will have at least 1 severe VOC, which typically presents as episodes of pain and inflammation at 1 or more sites, of varying degrees of severity, and occurring at varying intervals throughout life. These pain crises, as VOC episodes are also known, are the clinical hallmark of SCD, and are responsible for the vast majority of hospitalizations (>90%), and result in significant morbidity, mortality, and interruption of daily functioning. The onset of pain is unpredictable, and has been described as periodic, self-limited episodes of excruciating musculoskeletal pain (although visceral, soft tissue, and other locations have been reported), occurring as early as 6 months of age. In addition, readmission to the hospital for recurring or repeat episodes of VOC within a short time of discharge is common, with reports of up to 16% of patients readmitted within one week. Other problems include ischemic and hemorrhagic stroke, acute chest syndrome, splenic or hepatic sequestration, dactylitis, osteonecrosis, priapism, leg ulcers, and nephropathy. Most SCD-related deaths occur during acute VOC, and are due to acute chest syndrome, stroke, or multi-organ failure. Patients can become symptomatic with pain, infection, or splenic sequestration as early as 6 months of age; thus, VOCs are an important cause of morbidity and mortality throughout life, resulting in disruption of the individual's education, psychosocial development, and employment as well as causing severe pain, hospitalization, and premature death.

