    - Subjects may be included if treated as an outpatient within the past 48 hours for the same VOC episode
  11. Recent (within the past 90 days) cerebrovascular accident, transient ischemic attack, or seizure
  12. pRBC transfusions in the past 14 days
  13. Systemic steroid therapy within 48 hours prior to enrollment or expectation that therapy may be used during the study (inhaled or topical steroids are allowed)
  14. For those on chronic or long-acting opioids, a change in dose in the past 14 days OR pain requiring medical attention in the past 14 days (change in opioid medication for acute pain in the past 48 hours and directly related to this VOC admission is allowed)

15. Greater than 5 episodes of hospitalization for VOC in the past 6 months (180 days)
16. Medical or psychiatric condition that, in the opinion of the investigator, may pose a risk to the subject for participation or interfere with the conduct or results of the study
17. Currently receiving, or has received within the previous 4 weeks, any other investigational agent
18. Previous administration of GMI-1070
19. Expectation that the subject will not be able to be followed for the duration of the study
20. Pregnant or lactating female; or female of childbearing potential or male unable or unwilling to comply with birth control methods or abstinence during the course of the study
21. Active use of illicit drugs and/or alcohol dependence, as determined by the investigator

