## **5 STUDY DRUG AND CONCOMITANT TREATMENTS**

### **5.1 GMI-1070 and Placebo**

#### **5.1.1 Description**

The official product name, as indicated in the Investigator's Brochure, is 'GMI-1070 Injection, 30 mg/mL,' and will be referred to as 'GMI-1070' in this protocol. For further details regarding the exact composition of the product, please refer to the Investigator's Brochure.

Study drug will be supplied in vials containing 8.3 mL of sterile solution for IV administration. Active vials will contain GMI-1070 at 30 mg per mL; placebo vials will contain 8.3 mL of sterile vehicle (phosphate-buffered saline pH 6.5 [PBS]).

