#### **5.1.5 Blinding**

GMI-1070 will be supplied as open-label vials and a third-party design for blinding will be employed. The subject, the Sponsor, the CRO and all other study personnel in direct contact with study subjects will be blinded as to treatment allocation. The pharmacist (or designee) will be unblinded, and will prepare and label all study drug/placebo in a blinded manner to maintain the blind for all other personnel. Study drug/placebo syringes will be covered with opaque tape or similarly effective blinding method, IV bags will be covered, and colored tubing sleeves will be supplied for IV tubing.

Unblinding by study site personnel for AEs may only be performed in emergencies where knowledge of the subject's treatment assignment is essential for further management of the subject's medical care. Unblinding a subject's treatment assignment by the investigator or study site personnel under any other circumstances will be considered a protocol violation.

The investigator should make every effort to contact the CRO's Medical Monitor prior to unblinding a subject's treatment assignment. Emergency unblinding for AEs will be performed by the CRO Medical Monitor. Alternatively, if required, emergency unblinding for AEs may be done through the pharmacist responsible for preparation of

the drug. This may be performed only if the subject's well-being requires immediate knowledge of the subject's treatment assignment.

[figure not shown]
In the event of any unblinding, emergency or accidental, the CRO's Medical Monitor must be notified in writing within 1 working day, and the unblinding must be documented in the medical record at the investigative site as well as on the CRF. The date, time, and reason for breaking the blind must be recorded in the medical record.

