### **6.1.1 Pre-study Identification of Potential Study Subjects**

Investigators are encouraged to identify subjects with VOC who are likely to be admitted, and approach them for consent and eligibility criteria early in the process of VOC care. Subjects with a history of frequent admissions for painful VOC in the past 12 months, and identified during routine clinical care as potentially eligible for study participation, may be approached with educational information about the study. Such education will not replace the need to obtain informed consent (and assent, where applicable) in accordance with applicable regulations and ICH E6 prior to administration of any study related procedures.

Where possible and as appropriate, subjects who are eligible for study participation should have admission procedures expedited to allow for early study enrollment and prompt management of VOC per study procedures.

All subjects should be dosed with the first dose of study drug within 24 hours of initial medical evaluation in the Emergency Department/clinic. Any initial dose of study drug administered more than 24 hours after initial medical evaluation will be considered a protocol deviation.

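### Exclusion 18 turns on active treatment received, so a blinded site cannot apply it to a subject already randomized in this trial, and no other criterion bars that subject

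*Protocol*

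**What the plan says.** Exclusion 18 reads, in full, "Previous administration of GMI-1070" (protocol Section 4.3, repeated in the synopsis). Section 5.1.1 reserves the name GMI-1070 for the active product and describes placebo separately: "Active vials will contain GMI-1070 at 30 mg per mL; placebo vials will contain 8.3 mL of sterile vehicle". Elsewhere the protocol writes of study drug when it means either arm.

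The nearest other criteria do not fill the gap:
- Exclusion 17 applies to a person who "has received within the previous 4 weeks, any other investigational agent", so it does not reach earlier participation in this trial.
- Exclusion 10 looks back 14 days for VOC care.
- Exclusion 14 also looks back 14 days, and only for subjects on chronic or long-acting opioids.
- Exclusion 15 still allows up to 5 VOC hospitalizations in 180 days.

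On blinding, Section 5.1.5 states: "The subject, the Sponsor, the CRO and all other study personnel in direct contact with study subjects will be blinded as to treatment allocation". At the site, "The pharmacist (or designee) will be unblinded". Outside an emergency, unblinding "by the investigator or study site personnel under any other circumstances will be considered a protocol violation". Section 6.1.2 has the investigator or a qualified designee review eligibility before randomization.

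Section 1.2 says that "readmission to the hospital for recurring or repeat episodes of VOC within a short time of discharge is common", and Section 6.3.6.1 likewise expects repeat episodes after discharge.

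**The concern.** An eligibility rule has to be checkable by the person who applies it. For a former participant of this trial, Exclusion 18 depends on a fact that the investigator is forbidden to know. The protocol does not say what the site should do instead, and about 20 sites may answer differently.

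Two things are at stake. The first is the blind. The primary endpoint uses self-reported pain scores and the subject's and physician's statements of readiness for discharge, so a returning subject whose earlier arm can be inferred is no longer a naive participant. The second is independence. The primary ANCOVA (Section 8.2.3.1) and the sizing at about 38 per group (Section 8.3.2) treat each record as a separate person, and no provision covers someone who appears twice. Eligibility is set in the protocol, so a later analysis plan cannot repair it.

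**Working it through.** **The passages together.** Take a subject randomized earlier in this trial who presents with a new crisis more than 14 days after the last VOC care and meets all other criteria.

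1. Exclusion 18 is met if the earlier course was active and not met if it was placebo.
2. Exclusions 10, 14, 15 and 17 do not remove the subject. The inclusion criteria and Section 5.1.4 (allocation) do not mention earlier participation.
3. The person judging eligibility is blinded to the earlier course, and so are the subject, the sponsor and the CRO.
4. Three courses remain:
   - *Apply the rule literally*, for example by asking the pharmacist. Under 1:1 allocation the chance that the earlier course was placebo is 0.5 to a blinded observer. A pass moves it to 1 and a fail moves it to 0, so the answer itself is the unblinding. Only former placebo subjects re-enter.
   - *Guess.* Acceptance reveals nothing, but former active subjects may re-enter against the criterion.
   - *Decline every former participant.* The blind holds, but by a rule that the protocol does not contain.

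**The plan's own power figures (Section 8.3.2).** Inputs: placebo mean 103 h, common SD 60 h, 38 per group, 2-sided alpha 0.045. The noncentrality is δ / (SD × √(2/n)).
- 43.8% decrease: δ = 0.438 × 103 = 45.114 h, and 45.114 / (60 × √(2/38)) = 3.28. Power is 0.898 (normal) or 0.890 (noncentral t). The plan states 89%.
- 40% decrease: δ = 0.40 × 103 = 41.2 h. Power is 0.839 (normal) or 0.828 (t). The plan states 83%.

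Both figures reproduce.

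**Size of the duplication.** The protocol gives no re-enrolment rate, so the number k of repeat records is an assumption.
- Excess records: 2/76 = 2.6% and 6/76 = 7.9%, about 3% to 8%.
- Power for the 43.8% decrease if repeat records are given no weight and are spread evenly over the arms, so n = (76 − k)/2 per group:

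| k | n per group | Power (t to normal) |
|---|---|---|
| 0 | 38 | 0.890 to 0.898 |
| 2 | 37 | 0.882 to 0.891 |
| 4 | 36 | 0.873 to 0.882 |
| 6 | 35 | 0.863 to 0.873 |

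At k = 6 the loss is about 2.5 to 2.7 percentage points. The matter is therefore one of blinding, independence and uniform application, not of power.

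**The case against.** The strongest reply is that the protocol, read as a whole, already leads to the right result. Table 1 requires every eligibility criterion to be met before randomization, and Section 5.1.5 forbids non-emergency unblinding. An investigator who cannot certify Exclusion 18 should therefore not enrol the person. Section 4.4 also lets the site ask the sponsor for clarification in individual cases. Re-enrolment is nowhere described, and Section 6.3.6.1 treats a recurrence after discharge as an adverse event.

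Much of this stands. Re-enrolment is open by silence, not by permission, and a cautious site keeps the blind. But that outcome has to be inferred. The sponsor, being blinded too, cannot settle a case on the facts without the assignment being disclosed to it.

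Some stronger readings are tempting, and the document does not support them:
- *Every accepted re-entry reveals an earlier placebo assignment.* This holds only where the rule is applied literally, not where a site guesses.
- *The duplication is one-sided.* Under guessing, former active subjects may return as well. Even under literal use, second entries would be randomized 1:1, so about half of the second records would fall in the active arm.
- *The protocol's recurrence figures give the size.* The 16% readmission figure in Section 1.2 is for one week, a period that Exclusion 10 generally blocks. The figure of about 60% is the yearly share of SCD-SS patients with a severe crisis. Neither is a re-enrolment rate.
- *Recruitment is aimed at repeat patients.* Section 6.1.1 says only that "Subjects with a history of frequent admissions for painful VOC in the past 12 months" may be given educational information, and Exclusion 15 removes the most frequent admitters.
- *Twice the number of repeaters is affected.* Counting both records of each person overstates the matter, since the first record is legitimate.

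**Conclusion.** The point holds as a defect in one criterion. For a subject already randomized in this trial, Exclusion 18 either cannot be determined by the blinded investigator or discloses the earlier assignment when it is determined. No other criterion closes the gap. This is a stated rule that does not work under the trial's own blinding, in a disease where the protocol itself expects patients to return.

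The scope is narrow. Receipt of GMI-1070 in the open-label study in stable SCD (GMI-1070-103) can be established, so the criterion works there. The size rests on an assumed 2 to 6 re-enrolled persons, and the true number may be zero if sites decline all former participants. No alpha, sample size or stated power figure is wrong because of it. Severity is minor to moderate.

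**What to change.** In both the synopsis and Section 4.3, replace Exclusion 18 with: *Previous randomization in this study, or previous administration of GMI-1070 in any study.*

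A blinded site can check the first part from its own records or the subject's history without any treatment assignment. The second part keeps the existing bar for earlier studies. The change is one line of amendment text and leaves the planned number of subjects and the alpha as they are. The only cost is the loss of a few repeat patients, who should not count as new subjects in any case.

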#### 4.4 Withdrawal of Subjects

A subject is free to withdraw from the study at any time for any reason without prejudice to their future medical care by the physician or at the institution.

The Investigator or Sponsor may also withdraw the subject at any time. The primary reason for withdrawal must be recorded in the medical record and on the withdrawal case report form (CRF). If a subject is withdrawn for more than one reason, each reason should be documented in the medical record and the most medically significant reason should be noted on the CRF.

Reasons for withdrawal may include:

- If consent is withdrawn or the subject refuses to continue treatment and/or procedures/observations
- Occurrence of unmanageable AEs or if the subject requires concomitant medication disallowed under this protocol (refer to Section 5.2)
- If clinically significant and concerning changes in any clinical or laboratory measurements warrant withdrawal as determined by the Investigator (refer to Section 6.3.6.2 for a description of clinical laboratories in the context of adverse events)
- If the subject becomes pregnant
- For other reasons (eg, significant protocol violation, non-compliance)

The withdrawal of a subject from the study should be discussed where possible with the Medical Monitor before the subject stops study drug. Subjects withdrawn will not be replaced. Any comments (spontaneous or elicited) or complaints made by the subject and the reason for termination, date of stopping study drug, and the total amount of study drug administered must be recorded in the medical record and transcribed onto the CRF.

Subjects who prematurely stop administration of study drug but continue on the study will continue to be followed as per the procedures outlined in Table 1 up to Day 28.

All efforts will be made to obtain safety data, assigned PK samples, and other endpoint data from subjects, and these data will be included in the analysis.

Subjects who withdraw early from the study, will be encouraged to have all Day 28 evaluations, and any PK evaluations due at the time they withdraw, completed at the time of study withdrawal.

If a subject is unintentionally unblinded, study data collection should continue and the subject should continue to receive study drug.

If a subject is lost to follow-up after discharge from the hospital, at least three documented attempts to contact and see the subject must be made, one of which must include sending a certified letter to the subject's last known address requesting that they return to the study site for final safety evaluations.

The Sponsor may be contacted if clarification is required on a case-by-case basis.

#### **4.5 Study Termination**

The Sponsor reserves the right to terminate the study at any time. A description of study termination based on safety concerns is described in Section 6.3.6.4.

## **5 STUDY DRUG AND CONCOMITANT TREATMENTS**

### **5.1 GMI-1070 and Placebo**

#### **5.1.1 Description**

The official product name, as indicated in the Investigator's Brochure, is 'GMI-1070 Injection, 30 mg/mL,' and will be referred to as 'GMI-1070' in this protocol. For further details regarding the exact composition of the product, please refer to the Investigator's Brochure.

Study drug will be supplied in vials containing 8.3 mL of sterile solution for IV administration. Active vials will contain GMI-1070 at 30 mg per mL; placebo vials will contain 8.3 mL of sterile vehicle (phosphate-buffered saline pH 6.5 [PBS]).

#### **5.1.2 Dosing Administration**

After consent (and assent, where applicable) has been given and documented and the subject meets all inclusion/exclusion criteria, a written authorization (prescription/order/instruction signed by the investigator, who should be a study physician listed on Form Food and Drug Administration [FDA] 1572), is required prior to providing any subject with study drug.

The pharmacist will not be blinded, but all study personnel in direct contact with the subject will be blinded. Active drug will be labeled “GMI-1070 Injection, 30 mg/mL,” and will be administered as a loading dose of 40 mg/kg followed by 20 mg/kg every  $12 \pm 2$  hours for up to 7 days (maximum of 15 doses including the loading dose). Placebo will be labeled “PBS Placebo, 8.3 mL/vial,” and will be administered as a loading dose of volume equivalent to that of active drug, followed by a maintenance dose of volume equivalent to that of active drug every  $12 \pm 2$  hours for up to 7 days (maximum of 15 doses including the loading dose).

Study drug administration will occur at a steady rate over a period of 20 minutes from the start of the IV infusion, and will be followed by a saline or heparin flush (saline preferred) to ensure clearance of the IV tubing of any remaining study drug. New tubing is to be used with each administration of study drug. Study drug should not be administered concurrently through the same IV line with any medications, or with IV solutions other than saline-based solutions.

The planned schedule for dosing every  $12 \pm 2$  hours should remain as *planned*, irrespective of adjustments for timing based on the 2 hour window for dosing. Dosing schedule should not be adjusted for actual dosing times. For example:

**Table 6. Sample Dosing Schedule**

Dose	Planned Time	Actual Time
First dose (am)	9 am	9 am
Second dose (pm)	9 pm	10 pm
Third dose (am)	9 am	8:30 am
Fourth dose (pm)	9 pm	10:30 pm

### 5.1.3 Discontinuation of Study Drug

Subjects will be treated with study drug until they meet the following criteria for resolution of VOC:

- Sustained decrease in pain score of at least 1.5 cm out of 10 cm since baseline; AND transition to oral pain medications per hospital procedures (subject is on no IV pain meds)
- OR readiness for discharge as stated by the physician and subject
- OR discharge to home

For the purposes of this study, ‘sustained’ is defined as 2 consecutive pain scores at least 4 hours apart as reported by the subject on a VAS; ‘baseline’ is defined as the pain score just prior to the first dose of study drug as reported by the subject on the VAS.

Study drug should be discontinued if any of the following medical changes take place, and study evaluations should continue to be performed as outlined in Table 1:

- Subject is transferred to ICU for any medical reason

- Acute chest syndrome is diagnosed
- Acute stroke, or other acute CNS changes
- Fever >39° C (102.2° F); fever with negative chest radiograph does not require discontinuation of study drug unless determined to be medically appropriate by the investigator
- Elevated WBC >35,000/mm^3
- No improvement in VOC (as determined by the investigator, based on VAS and opioid or pain medication requirements and the judgment of the investigator) after 5 days of study drug
- Unexpected rise in creatinine, consistent with acute renal failure
- Pregnancy

Note: If it has been determined that study medication should be stopped no weaning of study medication will take place.

#### **5.1.4 Allocation of Subjects to Treatment**

Subjects will be randomized in a 1:1 ratio to receive either GMI-1070 or placebo. Randomization blocks will be stratified by site using an IVRS. Instructions on use of the IVRS will be included in the Study Reference Manual.

Once IRB/IEC approval for Amendment 3 (Protocol Version 4.0) is received, all new subjects should be enrolled at the new dose level of GMI-1070 or placebo.

#### **5.1.5 Blinding**

GMI-1070 will be supplied as open-label vials and a third-party design for blinding will be employed. The subject, the Sponsor, the CRO and all other study personnel in direct contact with study subjects will be blinded as to treatment allocation. The pharmacist (or designee) will be unblinded, and will prepare and label all study drug/placebo in a blinded manner to maintain the blind for all other personnel. Study drug/placebo syringes will be covered with opaque tape or similarly effective blinding method, IV bags will be covered, and colored tubing sleeves will be supplied for IV tubing.

Unblinding by study site personnel for AEs may only be performed in emergencies where knowledge of the subject's treatment assignment is essential for further management of the subject's medical care. Unblinding a subject's treatment assignment by the investigator or study site personnel under any other circumstances will be considered a protocol violation.

The investigator should make every effort to contact the CRO's Medical Monitor prior to unblinding a subject's treatment assignment. Emergency unblinding for AEs will be performed by the CRO Medical Monitor. Alternatively, if required, emergency unblinding for AEs may be done through the pharmacist responsible for preparation of

the drug. This may be performed only if the subject's well-being requires immediate knowledge of the subject's treatment assignment.

[figure not shown]
In the event of any unblinding, emergency or accidental, the CRO's Medical Monitor must be notified in writing within 1 working day, and the unblinding must be documented in the medical record at the investigative site as well as on the CRF. The date, time, and reason for breaking the blind must be recorded in the medical record.

